9.2 Responsibility for Analyses/In-house Blinding

The statistical analysis of the data obtained from this study will be the responsibility of the Clinical Biostatistics department of the Sponsor.

This study is being conducted as a randomized, open-label study, ie, participants, investigators, and Sponsor personnel will be aware of participant treatment assignments after each participant is enrolled and treatment is assigned.

The Clinical Biostatistics department will generate the randomized allocation schedule for study treatment assignment. The algorithm for the randomized allocation of subjects will be implemented in an interactive response technology by a study vendor.

9.3 Hypotheses/Estimation

Objectives of the study are stated in Section 3. This is an estimation study, and no formal hypothesis testing will be performed.

9.4 Analysis Endpoints

Immunogenicity and safety endpoints that will be evaluated for between-treatment differences are listed below.

9.4.1 Immunogenicity Endpoints

Primary immunogenicity analysis endpoints include:

- GMTs of anti-HPV 6, 11, 16, 18, 31, 33, 45, 52, and 58 measured by cLIA at 4 weeks Postdose 2 of 9vHPV vaccine.
- GMCs of SARS-CoV-2 spike protein-specific binding antibodies at 4 weeks Postdose 2 of mRNA-1273 vaccine.

Secondary immunogenicity analysis endpoints include:

- Seroconversion to HPV Types 6, 11, 16, 18, 31, 33, 45, 52, and 58 at 4 weeks Postdose 2 of 9vHPV vaccine. Seroconversion is defined as changing from cLIA anti-HPV seronegative prevaccination with 9vHPV vaccine to seropositive at 4 weeks Postdose 2 of 9vHPV vaccine.
- Seroresponse to SARS-CoV-2 at 4 weeks Postdose 2 of mRNA-1273 vaccine. Seroresponse is defined as ≥ 4 -fold rise in SARS-CoV-2 spike protein-specific binding antibody concentration from baseline to 4 weeks Postdose 2 of mRNA-1273 vaccine. If the baseline SARS-CoV-2 spike protein-specific binding antibody concentration is less than the LLOQ of the SARS-CoV-2 ECL assay, a ≥ 4 -fold rise is defined as SARS-CoV-2 spike protein-specific binding antibody concentration $\geq 4 \times$ LLOQ of the SARS-CoV-2 ECL assay.

9.4.2 Safety Endpoints

Safety and tolerability will be assessed by clinical review of all relevant parameters, including AEs and body temperature measurements postvaccination.

The safety analysis endpoints that address the primary objective include:

- Solicited injection-site AEs Days 1 through 7 postvaccination
- Solicited systemic AEs Days 1 through 7 postvaccination
- SAEs Days 1 through 28 postvaccination
- Serious vaccine-related AEs observed any time during the study

9.5 Analysis Populations

9.5.1 Immunogenicity Analysis Population

The PPI population will serve as the primary population for the analysis of immunogenicity relating to 9vHPV vaccination. The PPI population is HPV type-specific. The PPI population consists of all randomized participants who:

1. Have received all vaccinations planned within the context of the study with the correct dose of the 9vHPV vaccine and each vaccination visit has occurred within day ranges acceptable for statistical analysis (see [Table 7](#) for vaccination visits day ranges acceptable for statistical analysis).
2. Were seronegative by HPV-9 cLIA to the appropriate HPV type pre-9vHPV vaccination (see [Table 8](#) for serum collection day ranges acceptable for statistical analysis).
3. Have evaluable serology results based on serum sample collected within 21 to 49 days Postdose 2 of 9vHPV vaccination.
4. Have no protocol deviations that could interfere with the evaluation of participant's immune response to 9vHPV vaccination.

The mRNA-1273 per-protocol (mRNA-1273-PP) population will serve as the primary population for the analysis of immunogenicity relating to mRNA-1273 vaccination. This population consists of all randomized participants who:

1. Have received all vaccinations planned within the context of the study with the correct dose of mRNA-1273 and each vaccination visit has occurred within day ranges acceptable for statistical analysis (see [Table 7](#) for vaccination visits day ranges acceptable for statistical analysis).

2. Have evaluable serology results based on serum sample collected within 21 to 42 days Postdose 2 of mRNA-1273 vaccine.
3. Have no protocol deviations that could interfere with the evaluation of participant's immune response to mRNA-1273 vaccine.

Table 7 Acceptable Day Ranges for Vaccination Visits

Vaccination Dose	Vaccination Visit Window as Specified in the SoA (Relative to Vaccination Dose 1)	Day Range for Inclusion in Statistical Analysis (Relative to Vaccination Dose 1)
Dose 1		
9vHPV vaccine	0	0
mRNA-1273	0	0
Dose 2		
9vHPV vaccine	6 months ± 4 weeks	148 to 218 days
mRNA-1273	28 to 42 days	21 to 42 days
HPV=human papillomavirus; RNA=ribonucleic acid; SoA=schedule of activities		

Table 8 Acceptable Day Ranges for Collection of Serum Samples

Study Time	Target Collection Day	Day Range for Inclusion in Statistical Analysis
Predose 1 (target collection days and day ranges are relative to vaccination dose 1)		
9vHPV vaccine	0	-14 to 0
mRNA-1273	0	-14 to 0
Postdose 2 (target collection day and day range are relative to vaccination dose 2)		
9vHPV vaccine	28 days	21 to 49 days
mRNA-1273	28 days	21 to 42 days
HPV=human papillomavirus; RNA=ribonucleic acid; SoA=schedule of activities		

9.5.2 Safety Analysis Population

Safety analyses will be conducted in the APaT population, which consists of all randomized participants who received at least 1 dose of any study vaccine. Participants will be included in the treatment group corresponding to the study vaccine they actually received for the analysis of safety data using the APaT population. This will be the treatment group to which they are randomized except for participants who received incorrect vaccination regimen for the entire vaccination period; such participants will be included in the treatment group corresponding to the vaccination regimen actually received.

9.6 Statistical Methods

9.6.1 Immunogenicity Analysis Methods

9.6.1.1 Estimation of Immune Response Relating to HPV

Anti-HPV titers reported as less than the HPV type-specific LLOQ will be replaced by a numeric value equal to half of the HPV type-specific LLOQ in analyses of immunogenicity.

For each of HPV Types 6, 11, 16, 18, 31, 33, 45, 52, and 58, the primary objective relating to response to HPV vaccination at 4 weeks Postdose 2 will be evaluated. Separately for each HPV type, the GMTs with 2-sided within-group 95% CIs and GMT ratio with corresponding 2-sided 95% CI will be calculated using an analysis of variance model with a response of log individual anti-HPV titers and a fixed effect for the vaccination groups ([Table 9](#)).

9.6.1.2 Estimation of Immune Response Relating to SARS-CoV-2

The primary objective relating to response to mRNA-1273 vaccination at 4 weeks Postdose 2 will be evaluated. The analysis methods are the same as those that will be used for primary objective 1 (see Section 9.6.1.1).

SARS-CoV-2 spike protein-specific binding antibody concentrations reported as less than the LLOQ of the ECL assay will be replaced by a numeric value equal to half of the LLOQ in analyses of immunogenicity.

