2.3 Benefit/Risk Assessment

It cannot be guaranteed that participants in clinical studies will directly benefit from treatment during participation, as clinical studies are designed to provide information about the safety and effectiveness of an investigational medicine.

A 2-dose schedule with a 6- to 12-month interval between doses is approved for HPV vaccines and recommended in many countries for individuals 9 to 14 years of age [World Health Organization 2017] [Meites, E., et al 2016]. This study is designed to enroll individuals before they age out of the recommended target population for 2-dose schedules and to enable completion of a 2-dose vaccine series before increased risk of exposure to HPV. In this study, all participants will receive 2 doses of the 9vHPV vaccine 6 months apart.

The 9vHPV vaccine has been shown to be efficacious in preventing persistent anogenital HPV infection and disease associated with HPV Types 6, 11, 16, 18, 31, 33, 45, 52, and 58. The frequency, severity, and magnitude of AEs identified in previous studies and post marketing surveillance support a favorable benefit to risk analysis for the 9vHPV vaccine in the study population.

All participants will also receive a 2-dose regimen of mRNA-1273 vaccine. The frequency, severity, and magnitude of AEs identified in a previous clinical study support a favorable benefit to risk analysis for the mRNA-1273 vaccine in all studied populations. The mRNA-1273 vaccine has been shown to be efficacious in preventing COVID-19 illness in adolescents and adults. In the setting of an ongoing pandemic with increasing numbers of adults completing COVID-19 vaccination, preadolescents and young adolescents specifically represent a growing proportion of new COVID-19 cases reported to the US CDC and have been shown to contribute to household transmission [Lessler, J., et al 2021]. Individuals <18 years of age are estimated to account for approximately 20% of COVID-19 cases in all regions of the US, with growing recognition that primary vaccination series in this population will increasingly include preadolescents and young adolescents who were previously infected [Cull, B. 2022]. In the setting of continued SARS-CoV-2 pandemic transmission, a population seronegative for SARS-CoV-2 may be challenging to recruit and enroll.

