5.2 Exclusion Criteria

The participant must be excluded from the study if the participant:

Medical Conditions

1. *Has a fever (defined as oral temperature $\geq 100.0^{\circ}$ F or $\geq 37.8^{\circ}$ C) within the 24-hour period prior to the Day 1 visit.
2. Has a history of severe allergic reaction (eg, swelling of the mouth and throat, difficulty breathing, hypotension, or shock) that required medical intervention.
3. Is allergic to any component of the 9vHPV or mRNA-1273 vaccine, including aluminum, yeast, or BENZONASE™ (nuclease, Nycomed [used to remove residual nucleic acids from 9vHPV vaccine and other vaccines]). For this exclusion criterion, an allergy to vaccine components is defined as an allergic reaction that met the criteria for severe AEs or SAEs defined in Appendix 3.
4. Has a condition that is a contraindication to vaccination as indicated in the package insert of 9vHPV vaccine or EUA prescribing information of mRNA-1273 vaccine.
5. Has known thrombocytopenia or any coagulation disorder that would contraindicate intramuscular injections.
6. Is currently immunocompromised or has been diagnosed as having congenital or acquired immunodeficiency, HIV infection, lymphoma, leukemia, systemic lupus erythematosus, rheumatoid arthritis, juvenile rheumatoid arthritis, inflammatory bowel disease, or other autoimmune condition.
7. Has a history of splenectomy.
8. Has a history of myocarditis and/or pericarditis.
9. Is, at the time of signing informed consent/assent, a user of recreational or illicit drugs or has had a recent history (within the last year) of drug or alcohol abuse or dependence at the discretion of the investigator. Alcohol abusers are defined as those who drink despite recurrent social, interpersonal, and/or legal problems because of alcohol use.
10. Has a history of a positive test for HPV.
11. Has a history of a clinical or microbiological diagnosis of COVID-19, ≤ 90 days prior to Day 1 visit or history of MIS-C at any time prior to Day 1 visit.
12. (Female participants only) Is pregnant as determined by a serum pregnancy test or urine pregnancy test that is sensitive to at least 25 mIU/mL β -hCG.

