9.1 Statistical Analysis Plan Summary

Key elements of the statistical analysis plan are summarized below; the comprehensive plan is provided in Sections 9.2 to 9.12.

Study Design Overview	A Phase 3, Multicenter, Open-Label Study to Evaluate the Safety and Immunogenicity of 2-dose Regimens of 9vHPV and mRNA-1273 SARS-CoV-2 Vaccines Where the First Dose of Each Vaccine Are Given Concomitantly in Boys and Girls 9 to 11 Years of Age
Treatment Assignment	Study participants will be randomized in a 1:1 ratio between the Concomitant and Nonconcomitant Groups. No stratification will be implemented during randomization.
Analysis Populations	Immunogenicity: Per-protocol population Safety: APaT population
Primary Endpoint(s)	Immunogenicity: 1. cLIA anti-HPV 6, 11, 16, 18, 31, 33, 45, 52, and 58 titers. 2. SARS-CoV-2 spike protein-specific binding antibody concentration. Safety: 1. Solicited injection-site AEs Day 1 through Day 7 postvaccination. 2. Solicited systemic AEs Day 1 through Day 7 postvaccination. 3. SAEs Day 1 through Day 28 postvaccination. 4. Vaccine-related SAEs observed any time during the study.
Key Secondary Endpoints	Immunogenicity: 
Seroconversion to HPV Types 6, 11, 16, 18, 31, 33, 45, 52, and 58 based on cLIA.Seroresponse to SARS-CoV-2 based on SARS-CoV-2 ECL assay.
Statistical Methods for Key Immunogenicity Analyses	Evaluation of primary and secondary objectives will be performed separately for each immunogenicity parameter. Analysis of variance modeling will be used. The response variable is the natural logarithm of the relevant antibody titers and an indicator variable representing the concomitant vaccination group will be a fixed effect. Point estimates of the GMTs/GMC and corresponding within-group 95% CIs as well as geometric mean ratio and corresponding 95% CI of the geometric mean ratio will be derived from the estimate of the fixed effect.
Statistical Methods for Key Safety Analyses	By-treatment group summaries of safety endpoints will be provided in terms of treatment group-specific counts and proportions (or percent) of participants who are cases of particular safety endpoints. Confidence intervals of risk difference (difference in percent or proportions), when provided, will be calculated using the M&N method [Miettinen, O. and Nurminen, M. 1985].
Interim Analyses	No interim analyses are planned for this study.

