9.6.1.3 Estimation of Percent Seroconversion and Percent Seroresponse

The seroconversion percentages with respect to HPV Types 6, 11, 16, 18, 31, 33, 45, 52, and 58, and seroresponse percentage with respect to SARS-CoV-2, will be evaluated by computing point estimates and corresponding 2-sided 95% CIs. Calculation of the CI will be based on the exact binomial method proposed by Clopper and Pearson [CLOPPER, C. J. and PEARSON, E. S. 1934] ([Table 9](#)).

Table 9 Strategy for Analysis of Immunogenicity Endpoints

Endpoint/Variable (Description, Time Point)	Primary vs. Supportive Approach	Statistical Method	Analysis Population	Missing Data Approach
Primary Immunogenicity Objectives and Hypotheses				
GMTs of anti-HPV 6, 11, 16, 18, 31, 33, 45, 52, and 58 measured by cLIA at 4 weeks Postdose 2 of 9vHPV vaccine	P	Point estimate, 95% CI by ANOVA	Per-protocol	Observed data only
GMCs of SARS-CoV-2 spike protein-specific binding antibodies at 4 weeks Postdose 2 of mRNA-1273 vaccine	P	Point estimate, 95% CI by ANOVA	Per-protocol	Observed data only
Secondary Immunogenicity Objectives				
Seroconversion to HPV Types 6, 11, 16, 18, 31, 33, 45, 52, and 58 at 4 weeks Postdose 2 of 9vHPV vaccine	P	Point estimate, 95% CI value by Clopper and Pearson	Per-protocol	Observed data only
Seroresponse to SARS-CoV-2 at 4 weeks Postdose 2 of mRNA-1273 vaccine	P	Point estimate, 95% CI value by Clopper and Pearson	Per-protocol	Observed data only
ANOVA=analysis of variance; CI=confidence interval; cLIA=competitive Luminex Immunoassay; GMC=geometric mean concentration; GMT=geometric mean titer; HPV=human papillomavirus; P=primary; RNA=ribonucleic acid; SARS-CoV-2=severe acute respiratory syndrome coronavirus 2				

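### The SARS-CoV-2 GMC ratio is analysed without the Day 1 spike antibody value, although baseline-seropositive children are admitted; the estimate is valid but precision may be lost

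*Combined protocol and SAP*

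**What the plan says.** Section 9.6.1.1 estimates the HPV GMTs and their ratio "using an analysis of variance model with a response of log individual anti-HPV titers and a fixed effect for the vaccination groups". Section 9.1 describes the same model: "an indicator variable representing the concomitant vaccination group will be a fixed effect". Section 9.6.1.2 extends it to the SARS-CoV-2 GMC: "The analysis methods are the same as those that will be used for primary objective 1". Table 9 lists "Point estimate, 95% CI by ANOVA" for both primary immunogenicity endpoints. No covariate is named anywhere.

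The two per-protocol populations in Section 9.5.1 differ at baseline. For HPV, participants qualify if they "Were seronegative by HPV-9 cLIA to the appropriate HPV type pre-9vHPV vaccination". For mRNA-1273 the only serology criterion is "Have evaluable serology results based on serum sample collected within 21 to 42 days Postdose 2 of mRNA-1273 vaccine", with no condition on Day 1 serostatus.

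Eligibility does not remove prior infection. Exclusion criterion 11 begins "Has a history of a clinical or microbiological diagnosis of COVID-19" but reaches back only 90 days from Day 1, apart from MIS-C at any time. Section 2.3 expects that "primary vaccination series in this population will increasingly include preadolescents and young adolescents who were previously infected".

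Spike serum is drawn on Day 1 in both groups (Sections 1.3.1, 1.3.2 and 4.1). The plan uses that baseline value in the secondary seroresponse definition (Section 9.4.1), and Section 9.6.1.2 already gives a half-LLOQ substitution rule. Randomisation is unstratified (Section 6.3.2), and no subgroup analysis is planned (Section 9.10).

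**The concern.** In the HPV analysis everyone is seronegative at baseline for the type in question, so a group-only model leaves no serostatus difference unexplained. In the SARS-CoV-2 analysis the children may be a mix of previously infected and naive. If baseline antibody predicts the Postdose 2 level, that variation goes into the residual and widens the interval.

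At stake is the width of the interval, not its correctness. After the amendment this is an estimation study, so the interval is its main immunogenicity product. The SARS-CoV-2 ratio has the widest interval among the primary immunogenicity estimates: a log half-width of 0.494 in Table 11, against 0.279 to 0.338 for the HPV types. More enrolment cannot narrow it, because Section 4.2 says vaccine supply ends after 1Q2023. The analysis model is the remaining route to precision.

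**Working it through.** **Inputs from the documents.** SD of natural-log spike concentration 1.5 (Table 11, footnote c); 80 enrolled per group less 10% exclusion, giving 72 evaluable; two-sided 95% CI; true ratio 1.0 (Table 11, footnote b).

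**Inputs not in the documents, hence assumptions.** The correlation R between baseline and postdose values (with two covariates, the multiple correlation), the share of children seropositive at Day 1, and the postdose fold difference by serostatus.

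**Step 1: reproduce the plan's figure.**

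Half-width = t(0.975, 142) × 1.5 × √(2/72) = 1.977 × 1.5 × 0.1667 = 0.494.

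This matches Table 11, so the tabulated half-width is on the natural-log scale. The ratio CI is exp(±0.494) = 0.61 to 1.64. The same method, with SD = √ln(1 + CV²), reproduces the nine HPV rows to within rounding.

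**Step 2: add baseline covariates and charge for them.** With k covariates:

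Half-width = t(0.975, 142 − k) × 1.5 × √(1 − R²) × √(2/72) × √(1 + k/(142 − k − 1)).

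The last factor is the average cost of chance covariate imbalance. The equivalent number per group is 72 × (0.494/half-width)².

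| Model | R | Log half-width | Ratio CI | Equivalent n per group |
|---|---|---|---|---|
| Planned ANOVA | – | 0.494 | 0.61–1.64 | 72 |
| k = 1 | 0 | 0.496 | 0.61–1.64 | about 72 |
| k = 2 | 0 | 0.498 | 0.61–1.64 | 71 |
| k = 2 | 0.3 | 0.475 | 0.62–1.61 | 78 |
| k = 2 | 0.5 | 0.431 | 0.65–1.54 | 95 |

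With k = 2 the break-even R is about 0.12. The loss at R = 0 is 0.498/0.494 − 1, or about 0.7% of the width. The interval is about 4% narrower at R = 0.3 and 13% narrower at R = 0.5.

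**Step 3: serostatus as the only source of prediction.** For a seropositive share p, R² = p(1 − p)(ln fold)²/2.25. Half-widths use k = 2.

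| p | Fold difference | R² | Log half-width |
|---|---|---|---|
| 0.5 | 2 | 0.053 | 0.484 |
| 0.5 | 4 | 0.214 | 0.441 |
| 0.2 or 0.8 | 2 | 0.034 | 0.489 |
| 0.2 or 0.8 | 4 | 0.137 | 0.463 |

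A simulation of the two-covariate model at p = 0.5 (4,000 runs) also gave 0.484 and 0.441.

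**Step 4: what the SD of 1.5 represents.** Table 11 does not say whether it comes from a mixed or a baseline-negative population. If it is the SD within serostatus, then at p = 0.5 the total SD is √(2.25 + 0.25(ln 2)²) = 1.540 for a 2-fold difference, or √(2.25 + 0.25(ln 4)²) = 1.652 for a 4-fold difference. The unadjusted half-width would then be 0.507 or 0.544, against about 0.498 adjusted.

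**The case against.** The strongest reply is that nothing here is an error. The model is stated consistently, the ratio is unbiased under randomisation, and chance imbalance in serostatus is already covered by the CI. No margin, test or decision depends on the width. Observed GMCs and their ratio answer the objective directly, whereas an adjusted ratio need not equal the ratio of the observed GMCs. The sponsor plainly knew about prior infection, since it discusses it and uses baseline in the seroresponse definition. The gain may also be trivial: with a 2-fold difference the interval narrows by only 1% to 2%. Changing a primary method in an open-label study invites questions, and an adjusted ratio could instead be added as supportive through the supplemental SAP that Section 9 allows.

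Much of this stands. The planned analysis is valid, and the documents cannot establish the gain. The cost is also slightly higher if a missing-baseline indicator is used: with k = 3 and R = 0 the half-width is 0.4996, a 1.1% loss, and the break-even R is about 0.15.

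The balance does not change. The likely loss is about 1% of the width, against about 4% to 13% at correlations of 0.3 to 0.5. Keeping the unadjusted results as supportive preserves the observed GMCs. Fixing and dating the change before results are seen by group answers the open-label objection.

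**Conclusion.** The concern holds as a low-cost improvement that should be made, not as a correction of an error. The planned ratio and CI are valid, with the usual caveat about exclusions after randomisation in a per-protocol population.

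Adjustment would take the log half-width from 0.494 to between 0.498 (baseline predicts nothing) and 0.431 (R = 0.5). The upper end is worth about 23 more evaluable children per group (95 − 72). These figures rest on the stated SD of 1.5, on 72 evaluable per group, and on an assumed R. Section 2.3 reports no published data on vaccinating previously infected children, so R cannot be narrowed from the documents and the gain could be negligible. If the SD of 1.5 describes baseline-negative children, the unadjusted interval would be wider than Table 11 shows and the case for adjustment stronger. The point does not extend to HPV, where the population is restricted to baseline-seronegative children.

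**What to change.** Amend Sections 9.1 and 9.6.1.2 and Table 9 so that the SARS-CoV-2 GMC ratio comes from an ANCOVA on natural-log concentration, with these terms:

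- vaccination group;
- natural-log Day 1 spike concentration, using the half-LLOQ rule already stated;
- an indicator for a Day 1 value below LLOQ.

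State how a missing Day 1 result is handled, since the mRNA-1273 per-protocol population does not require one. One option is the pooled mean baseline plus a missing indicator, so that the adjusted and unadjusted analyses use the same children. Keep the unadjusted ANOVA GMCs, within-group CIs and ratio as supportive. A descriptive table of GMC and seroresponse by baseline status is optional.

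Date and justify the change before database lock and before any Postdose 2 spike results are summarised by group.

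The cost is a wording change to the protocol (the SAP is its Section 9), two degrees of freedom (three with a missing indicator), a missing-baseline rule, and adjusted means reported beside the observed GMCs. No sample or assay is added.
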